## 4 Trial design

This is a double-blinded, randomized, sham-controlled post-marketing (exploratory) trial to evaluate the therapeutic effect of five cycles of immunoabsorption every other day in 66 patients with CFS/ME, including patients with PACS-CFS. Two patient groups will be included (2:1), one receiving IA, one receiving a sham-apheresis.

A screening visit is planned up to max. 3 weeks (Day -42 to Day -21) before enrolment in the study to screen patients for eligibility (including blood and urine samples for safety parameters such as viral serology, pregnancy, drug and alcohol tests) and to assess demographics and medical history (table 1). In addition, cerebrospinal fluid and blood samples are taken to test for autoantibodies and markers of neurodegeneration or neuroinflammation. If a lumbar puncture was performed as part of the clinical routine within 6 months prior to the screening visit, it will not be repeated at screening. Patient reported outcome measurements such as Chalder Fatigue Scale, physical and autonomic function, quality of life and (in case of PACS-CFS) Post-COVID-19 Functional Status Scale questionnaires as well as Cognitive (MoCA and SDMT), physical (hand grip strength evaluation, 6MWT), and autonomic (Schellong-Test) assessments are performed at

screening or baseline visit. At baseline visit a detailed neuropsychological examination, and an assessment of physical function will be conducted.

Baseline assessments will be performed between Day -20 and -1 and in any case before the first IA cycle. These include a general and neurological physical examination assessing vital signs, ECG, body weight, repeating safety check for pregnancy. Blood samples for chemistry, hematology, coagulation and immunoglobulin titers are taken.

Patients are randomized either on Day -1 or Day 1 and a peripheral venous access (or Shaldon catheter) is implemented before the first IA cycle on Day 1 or Day 2 (Figure 1). Patients will be hospitalized at the clinical site from Day 1 to Day 9 or Day 10 and receive five IA treatments and medical visits including monitoring of coagulation every other day (i.e., on Days 1, 3, 5, 7, and 9 OR on Days 2, 4, 6, 8, and 10). If delays occur, the option to extend the in-hospital stay is available. Immunoabsorption can be postponed by one or more days.. Daily study nurse visits are scheduled including control of vital signs as well as questioning for AE(s).

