| Blood samples for monitoring of coagulation  | X   | X                |   |                 |                 |                 |                 |                 |                 |                 | X   |    | X                 |                  |                    |                   |
| Monitoring of IA (IgG)   |                   |                  | Before each and after last IA treatment     |                 |                 |                 |                 |                 |                 |                 |     |    |                   |                  |                    |                   |
| Blood samples for immunoglobulin titers (IgA, IgG, IgM)  |                   | X                |   |                 |                 |                 |                 |                 |                 |                 | X   |    | X                 |                  |                    | X                 |
| Adverse event questioning  |                   | X                | < ----- >                                   |                 |                 |                 |                 |                 |                 |                 |     |    |                   |                  |                    |                   |
| Concomitant Medications  |                   | X                | < ----- >                                   |                 |                 |                 |                 |                 |                 |                 |     |    |                   |                  |                    |                   |
| Procedures  |                   |                  |   |                 |                 |                 |                 |                 |                 |                 |     |    |                   |                  |                    |                   |
| Randomization  |                   | X                |   |                 |                 |                 |                 |                 |                 |                 |     |    |                   |                  |                    |                   |
| PVA or Shaldon catheter implementation   |                   |                  | X   |                 |                 |                 |                 |                 |                 |                 |     |    |                   |                  |                    |                   |

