| Chest X-ray after Shaldon catheter implementation (if applicable)  |                   |                  | X   |                 |                 |                 |                 |                 |                 |                 |     |    |                   |                  |                    |                   |
| Cranial MRI  |                   | X   |   |                 |                 |                 |                 |                 |                 |                 |     |    | X                 |                  |                    |                   |
| TheraSorb - Ig omni 5 adsorber cycles (IA active or IA sham)   |                   |                  | 5 IA treatments every other day             |                 |                 |                 |                 |                 |                 |                 |     |    |                   |                  |                    |                   |
| OCT  |                   | X                |   |                 |                 |                 |                 |                 |                 |                 |     |    | X                 |                  |                    |                   |
| Removal of Shaldon catheter after last IA cycle  |                   |                  |   |                 |                 |                 |                 |                 |                 |                 | X   |    |                   |                  |                    |                   |
| Lumbar puncture samples   | X                 |                  |   |                 |                 |                 |                 |                 |                 |                 |     |    | X    |                  |                    |                   |
| Blood samples for:
- autoantibodies 
- inflammatory markers (CRP, Ferritin, MBL, C3, C4), LDH, ACE
- SARS-CoV-2 antibody-status |                   | X                |   |                 |                 |                 |                 |                 |                 |                 |     |    | X                 |                  |                    | X                 |

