## 5 Analysis sets

### 5.1 Definitions

The modified **full analysis set (FAS)** consists of a modified intention-to-treat (mITT) population and will include all patients that were randomized and underwent at least one IA cycle (active or sham IA intervention).

The **per-protocol set (PPS)** comprises all subjects who completed five cycles of their assigned intervention (IA or sham IA) as planned and who completed the study without critical protocol deviations.

The **safety analysis set (SAS)** will include all patients that underwent at least one IA cycle (active or sham IA intervention). Patients will be analyzed according to the intervention they received.

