### 5.2 Application

The primary analysis is performed using the full analysis set (FAS), including the estimated values from multiple imputations for missing values. An analysis of the primary outcome using the PPS is used as a sensitivity analysis. All safety analyses will be done using the SAS (Safety analysis set).

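### The safety set starts at the first IA cycle, so an access complication that prevents any cycle is left out of the adverse event rates

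*SAP*

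**What the plan says.** Section 5.1 of the SAP defines the safety analysis set (SAS) as one that "will include all patients that underwent at least one IA cycle (active or sham IA intervention). Patients will be analyzed according to the intervention they" actually received. Section 5.2 adds: "All safety analyses will be done using the SAS (Safety analysis set"). The full analysis set in section 5.1 carries the same one-cycle condition, and no other safety population is defined.

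On timing, section 4 states: "Patients are randomized either on Day -1 or Day 1". It then says that "a peripheral venous access (or Shaldon catheter) is implemented before the first IA cycle on Day 1 or Day 2". The schedule of assessments (Table 1) lists "PVA or Shaldon catheter implementation" among the procedures for Day 1, followed by "Chest X-ray after Shaldon catheter implementation (if applicable"). The row "Adverse event questioning" is marked at baseline and runs on through the treatment period. Section 4 also provides for daily nurse visits in hospital that ask about adverse events.

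Section 9.4 plans Poisson incidence rates and incidence rate ratios, and a listing of all individual adverse events and serious adverse events. It does not name a population for the listing.

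**The concern.** A safety set of treated patients works well when nothing invasive happens between randomisation and first treatment. Here a trial procedure with its own risk sits in that gap. Table 1 ties a check to it, since a chest X-ray follows a Shaldon catheter. If a complication of the access means that the patient never starts a cycle, the patient does not meet the entry condition of the set in which the event should be counted. Entry then depends in part on not having had that complication.

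The trial evaluates immunoadsorption as a procedure, and the access is part of delivering it. With 44 and 22 patients planned, one serious procedural event is a visible part of the safety result. Section 7.3 names discontinuation due to treatment-emergent events as a safety endpoint, and a patient who stops for this reason before cycle 1 could not be counted under it.

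**Working it through.** No figure in the SAP bears directly on this point, so the check is mainly a trace of the text, followed by an illustration of scale.

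**Trace**

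1. Randomisation is on Day -1 or Day 1 (section 4). Venous access is placed before the first cycle, on the day of that cycle or earlier (section 4; Table 1 shows it on Day 1). There is therefore a state in which a patient is randomised and cannulated but not yet treated.
2. Membership of the SAS needs at least one active or sham cycle (section 5.1). A patient who never leaves that state is outside the set.
3. All safety analyses use the SAS (section 5.2). The incidence rates and rate ratios of section 9.4 therefore omit the patient from both the event count and the observation time.
4. The full analysis set does not pick the patient up, because it has the same condition.
5. The rule that patients are analysed by intervention received gives no arm to someone who received neither, so simply widening the set would leave this patient unallocated.
6. The event itself would be recorded, because adverse event questioning begins before cycle 1.

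**Effect of one event**

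Inputs: 44 patients in the IA arm (section 4.2). Assume that one has an access complication and never starts a cycle, and that the other 43 all do. The plan uses Poisson rates; simple proportions are used here because they show the same shift without assumed follow-up times. Intervals are exact (Clopper-Pearson).

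- Under the SAS as written: 0/43 = 0%. Upper limit = 1 − 0.025^(1/43) = 8.2%.
- With the patient counted: 1/44 = 2.3%. Lower limit = 1 − 0.975^(1/44) = 0.06%; upper limit = 12.0%.

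**How often this could happen**

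The SAP gives no rate for patients who are cannulated but never start a cycle. For an assumed per-patient risk p and n = 66, the expected number is 66p and the chance of at least one is 1 − (1 − p)^66.

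| Assumed p | Expected number of 66 | Chance of at least one |
|---|---|---|
| 0.5% | 0.33 | 28% |
| 1% | 0.66 | 48% |
| 2% | 1.32 | 74% |
| 3% | 1.98 | 87% |

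Here p is the risk of a complication that prevents treatment altogether, not the risk of any access complication. The higher rows are probably too high, because some patients have only a peripheral access and section 4 lets a cycle be postponed.

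**The case against.** The strongest reply is that the definition is conventional. Treated patients, analysed by treatment received, are the usual safety set, and sections 5.1, 5.2 and 7.3 do not contradict one another. That stands: this is an improvement to a standard definition and not a misstatement. The convention fits poorly here only because an invasive trial procedure precedes the event that defines the set.

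Four stronger readings are tempting, and the SAP does not support them.

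- *The patient vanishes from all safety reporting.* Section 9.4 promises a listing of all individual events and highlights those that lead to withdrawal. It may be meant to cover every randomised patient. Section 5.2 can be read as restricting it, but the SAP does not settle this. Only the omission from rates and rate ratios is certain.
- *A patient whose first cycle is aborted is also lost.* Section 5.1 requires five completed cycles for the per-protocol set but only that patients underwent one cycle for the SAS. The contrast suggests that a started cycle counts.
- *Any access complication before cycle 1 removes the patient.* Section 4 allows treatment to be postponed and the hospital stay to be extended. A patient who is treated later stays in the set.
- *The comparison between arms is biased.* The rule is the same in both arms, and access placement is described without distinguishing them. No direction of bias follows.

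The protocol is not at hand and may say how events before first treatment are reported. Even so, the SAP's own rule governs the rates that it plans.

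**Conclusion.** The point holds in a limited form. Followed as written, the plan leaves out of the adverse event rates and rate ratios any randomised patient whose access complication means that no cycle is ever started, and it leaves open whether the listings show that patient. The distortion is downward and affects the absolute rate of procedural events. It probably involves no more than one or a few patients: in the example, 0/43 in place of 1/44, with intervals that overlap widely. The frequency figures rest wholly on assumed risks and show scale only. The change is worth making because it is cheap and a single such event would matter in a trial of this size.

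**What to change.** In section 5.1, define the SAS as all randomised patients in whom placement of the study venous access was attempted or any part of an active or sham cycle was started. Analyse them by intervention received, or by assigned arm if no cycle was started. State that adverse events, and the observation time in the Poisson models, count from the access attempt. In section 9.4, state that the listings cover all randomised patients. Leave the full analysis and per-protocol sets as they are.

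The cost is SAP wording only, since adverse event questioning already starts at baseline. The downside is that the safety table may contain a few patients with no apheresis exposure, who can be identified in a footnote.

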### 5.2 Application

The primary analysis is performed using the full analysis set (FAS), including the estimated values from multiple imputations for missing values. An analysis of the primary outcome using the PPS is used as a sensitivity analysis. All safety analyses will be done using the SAS (Safety analysis set).

## 6 Trial centres

This is a single centre study with 66 patients.

## 7 Analysis variables

## 7.1 Demography and baseline characteristics

The following variables are assessed at baseline as additional patient characteristics:

Table 4: Demography and baseline characteristics

| Characteristic                         | Variable                            | Values  |
|--|-------------------------------------|---|
| demographics                           |                                     |   |
| Age at inclusion (years)               | dm_0010                             | number  |
| sex                                    | dm_0020                             | male, female, diverse   |
| Body weight (kg)                       | dm_0031                             | number  |
| Body height (cm)                       | dm_0032                             | number  |
| BMI (kg/m  )               | dm_0033                             | number  |
| Employment status                      | dm_0040                             | employed, self-employed, currently unable to work, pension, student, unknown  |
| Educational achievement                | dm_0050                             | No school-leaving certificate, lower secondary school leaving certificate (Hauptschule), higher secondary school leaving certificate (Realschule), grammar school (Gymnasium), completed vocational training, degree of a university of applied sciences, University, unknown |
| Self-reported predominant race         | dm_0061 / dm_0062 (other specified) | Caucasian, African, Asian, Unknown, Other, please specify   |
| Medical history                        |                                     |   |
| Pre-existing diseases                  | mh_0010                             | yes, no   |
| Pre-existing diseases: chapter         | mh_0021                             | e.g. diseases of the circulatory system   |
| Pre-existing diseases: group           | mh_0022                             | e.g. Pulmonary heart disease and Diseases of the pulmonary circulation  |
| Pre-existing diseases: subgroup        | mh_0023                             | e.g. Pulmonary embolism   |
| Pre-existing diseases: ICD-Code        | mh_0024                             | e.g. I26.-  |
| Pre-existing diseases: ICD-Description | mh_0026                             | e.g. Pulmonary embolism   |
| Concomitant medications                | cm_0021- cm_0026                    | Anatomical, therapeutically, chemical, ATC Code, active substance   |
| Smoking                                |                                     |   |
| Smoking status                         | mh_0051                             | Current smoker, former smoker, never smoker, unknown  |
| Years of smoking                       | mh_0052, mh_0054                    |   |

|   |                     |  |
|---|---------------------|--|
| Type of smoking                               | mh_0056             | e-cigarette, cigarette, other, unknown   |
| Number of cigarettes per day                  | mh_0058             |  |
| Known allergies                               | mh_0071             | yes, no  |
| Type of allergy                               | mh_0072-
mh_0083 | Pollen allergy, House dust mite allergy, Animal allergy, Hives, Sun allergy, Cross allergies, Insect venom allergy, Drug allergy |
| Anamnesis of infections                       |                     |  |
| SARS-CoV-2 diagnosis in connection to fatigue | imh_0011            | yes, no  |
| Other infection in connection to fatigue      | imh_0021            | yes, no  |
| Date of onset fatigue                         | imh_0031            |  |

## 7.2 Primary variable

The primary outcome variable is the Chalder Fatigue Scale (Chalder et al., 1993) (range 0-33) at day 60.

## 7.3 Secondary variables

### Safety related endpoints:

Occurrence of treatment emergent adverse events (TEAEs), serious adverse events (SAEs), and discontinuation due to TEAEs

Assessment of physical examinations, laboratory parameters, vital signs, and ECGs

### Clinical effectiveness related endpoints

- Chalder Fatigue Scale (Chalder et al., 1993) at End of Treatment (EOT) visit and at month 1, 4, and 6 after the completion of IA
- Post-COVID-19 Functional Status (PCFS) scale (Klok et al., 2020) at month 1, 2, 4, and 6 after IA completion (only in patients with PACS-CFS)
- the SF-36 physical domain (Ware & Sherbourne, 1992) at EOT visit and at month 1, 2, 4, and 6 after IA completion
- Fluge questionnaire (Fluge et al., 2011; Fluge et al., 2015) at month 1, 2, 4, and 6 after IA completion
- PEM frequency, strength and severity by PEM questionnaire (Cotler et al., 2018) at EOT visit and at month 1, 2, 4, and 6 after IA completion
- the Bell disabling scale (Bell, 1995) at EOT visit and at month 1, 2, 4, and 6 after IA completion
- the Compass-31 questionnaire (Sletten et al., 2012) at month 1, 2, 4, and 6 after IA completion
- Schellong Test (Fanciulli et al., 2019) at EOT visit and at month 2 and optional month 6 after IA completion
- hand grip strength test, at EOT and at month 2 and optional at month 6 after IA completion
- the 6 Minute Walking Test (6 MWT) ("ATS statement: guidelines for the six-minute walk test," 2002) at month 2 after IA completion
- optional neuropsychiatric assessment at month 2 after IA completion

- neurocognitive assessments (MoCA and SDMT) (Nasreddine et al., 2005) (Strober et al., 2020) at month 2 after IA completion
- quality of life (QoL) determined by the PROMIS questionnaire at month 1, 2, 4 and 6 after IA completion (Cella et al., 2019; Yang et al., 2019)
- PROMIS cognitive function short form 4a
- VLMT (verbal learning and memory test) (Helmstaedter et al., 2001)
- BVMT-R (brief visuospatial memory test revised) (Benedict, 1997)
- WAIS-IV (Wechsler adult intelligence scale) (Wechsler, 2008)
- TAP (Test of attentional performance) (Zimmermann & Fimm, 2004)
- LPS 50+ (Leistungsprüfungssystem (performance testing system) for 50 to 90 years old) (Sturm et al., 2015)
- TMT-A / B, Trail Making Test A / B (Reitan & Wolfson, 1993)
- RWT, Regensburger Wortflüssigkeits-Test (Regensburg Word Fluency Test) (Aschenbrenner et al., 2000)
- WST, Wortschatz-Test (Vocabulary test) (Schmidt & Metzler, 1992)

***Biomarker related endpoints:***

- biomarkers of autoimmune activity (autoantibody titers against neurotransmitter receptors; among others  $\beta$ 2-adeno-receptor- and muscarine- receptor-antibodies) in blood at month 2 and 6 and optional in cerebrospinal fluid at month 2 after IA completion
- immunostatus (differential blood, IgG, IgM, IgA fractions) in blood at EOT, at month 2 and 6 after IA completion
- immunoglobulin levels (including SARS-CoV-2 antibody titers and PCR, if applicable) at month 2 and 6 in blood and optional in cerebrospinal fluid at month 2 after IA completion
- inflammatory biomarkers in blood (CRP, ferritin, MBL, white blood cell count, complement factors, immunoglobulin level and subtype) at month 2 and 6 after IA completion
- autoantibodies against known or unknown neuronal epitopes (Stöcker- autoimmune-encephalitis panel and screening via immunofluorescent staining on mouse brain sections – in cooperation with separate project EA1/258/18) in blood and optional in cerebrospinal fluid after IA completion .
- neurofilament (NFL) in cerebrospinal fluid at month 2 after IA completion
- auto-antibody and vaccine titers in serum and cerebrospinal fluid as well as intrathecal synthesis (CFS) at month 2 after IA completion
- inflammatory biomarkers in cerebrospinal fluid (white cell count, total protein, CSF/serum quotients of albumin (Qalb), lactate, oligoclonal IgG bands (OCB), cytokines)) at month 2 after IA completion
- MRI parameter: grey matter volume, white matter volume, thalamus volume left and right, thalamic functional connectivity to sensomotoric cluster left and right, thalamic functional connectivity to visuo-occipital cluster left and right, EndoPAT Reactive Hyperemia Index (RHI). Volumetry is based on a high-resolution T1-weighted MPRAGE sequence (voxel size 1 mm isotropic, FOV 256 mm, TR = 2500 ms, TE = 2.64 ms). The functional connectivity measures are derived from a BOLD-sensitive resting-state EPI sequence (720 volumes, voxel size 2 mm isotropic, TR = 800 ms, TE = 37 ms, FOV 208 mm).
- OCT parameter: ganglion cell-inner plexiform layer (GCIPL), peripapillary retinal nerve fiber layer (pRNFL), foveal avascular zone (FAZ), vessel density
- CD11c-Expression: Mean fluorescence intensity (MFI) on total CD19 $^{+}$  B cells, Percentage of CD11c $^{-}$  cells within the CD19 $^{+}$  gate, CD11c MFI and %CD11c $^{-}$  specifically on IgD $^{-}$ CD27 $^{+}$  memory B cells (CD19 $^{+}$ IgD $^{-}$ CD27 $^{+}$  gate)
- IgM Expression: Mean fluorescence intensity (MFI) on total CD19 $^{+}$  B cells, Percentage of IgM $^{-}$  cells within the CD19 $^{+}$  gate, IgM MFI and %IgM $^{-}$  specifically on

IgDCD27+ memory B cells (CD19+IgDCD27+ gate), Activated Canonical Class-Switched Memory B Cells (aCSM), CD19+IgDIgMCD27+CD11c, Frequency quantification within total B cells or parent gates, Activated canonical class-switched memory B cells

Table 5: primary and secondary outcome variables

| Characteristic   | Variable            | Values   |
|--|---------------------|--|
| Primary outcome variable   |                     |  |
| Chalder Fatigue Scale at 2 months  | cfs_0001-cfs_0011   | 11 items with levels 0-3 each, sum score has to be calculated  |
| Secondary outcome variables  |                     |  |
| Efficacy related outcomes  |                     |  |
| Chalder Fatigue Scale at End of Treatment (EOT) visit and at month 1, 2, 4, and 6 after the completion of IA | cfs_0001-cfs_0011   | 11 items with levels 0-3 each, sum score has to be calculated  |
| Post-COVID-19 Functional Status (PCFS) scale   | pcfs_0020-pcfs_0050 | Ordinal scale, range 0 to 4 (0: no limitations, 4: severe limitations),  |
| SF-36 physical domain  | sf_0041-sf_0050     | 10 items, each scored with: no limitations (0 points), some limitations (5 points), severe limitations (10points), the sum will be calculated  |
| Fluge questionnaire  | ccc_0011-ccc_0131   | 5 domains with different number of items, domains: fatigue, pain, cognition, circulation, each item is scored from 0 to 10 according to the severity (10: highest severity), domains will be analyzed separately |
| Post-Exertional Malaise (PEM)  | pem_0021-pem_0110   | 11 items, 5 items scored 0 to 4 for frequency, 5 items scored 0 to 4 for severity, 1 item scored 0 to 6 for duration, sum score from 0 to 46   |
| Bell Score   | bell_0020           | 1 item with 11 statements, 0-100   |

|  |  |  |
|--|--|--|
|  |  | points (100: no symptoms, 0: severe symptoms)  |
| Compass-31   | com_0001-com_0031  | 31 items in 6 domains, score by domain are rescaled ranging from 0 to 100  |
| Schellong Test /POTS   | pst_0021-pst_0080  | Using items to evaluate if POTS is present (Increase in heart rate within 10 minutes of standing by at least 30 beats/minute above the level when lying down or, to at least 120 beats/minute absolutely, no pathological drop in blood pressure (i.e., systolic drop not more than 20 mm Hg and diastolic drop not more than 10 mm Hg), increasing symptoms of orthostatic intolerance) |
| 6 Minute Walking Test (6 MWT)  |  |  |
| MoCA   | moca_0011-moca_0110  | Score items, sum of maximum 30 or 31 points dependent on educational level   |
| Symbol Digit Modalities Test, SDMT   | sdmt_0020  | Item on number of correct remembered words after 90 seconds  |
| PROMIS-29, physical function, anxiety, depression, pain interference, pain severity, fatigue, sleep disturbance, ability to participate in social roles and activities | pfa11-pfa53, edanx01-edanx53, eddep04-eddep41, hi7, an3, fatexp41, fatexp40, sleep109, sleep116, sleep20, sleep44, srpper11_caps-srpper46_caps, pain9-pain34, global07 | each of the 7 domains will be scored separately, transformation in standardized t-values   |
| PROMIS cognitive function short form 4a  | pc2r-pc42r   | Sum score converted to t score   |
| Additional secondary outcome variables   |  |  |
| VLMT (verbal learning and memory test)   | vlmt_0011 – vlmt_0220  | total score : addition of the learning achievements of the 5  |

|   |                       |   |
|---|-----------------------|---|
|   |                       | rounds; delayed recall : number of words correctly recalled from the word list after a time delay; loss after delay : subtraction of the number of correctly recalled words in learning session 7 from the number of correctly recalled words in learning session 5; correct recognition : subtraction of the number of false positives and interference items from the number of correctly recognised words in the first list (i.e.: 18. recognition performance (W) - (19. interference + 20. false positives)). |
| BVMT-R (brief visuospatial memory test revised) | bmvt_0011 – bmvt_0150 | total score : addition of the points from all three trials; delayed recall : number of correctly remembered figures. (correct figure and correct place); percent retained : [delayed recall / (higher of trial 2 and trial 3)] x 100; recognition discrimination index : (recognition hits) - (recognition false alarms)  |
| WAIS-IV (Wechsler adult intelligence scale)     | wais_0011 – wais_0070 | forward : number of correctly repeated number sequences; backwards : number of number sequences correctly recited backwards; sequential : number of correctly sequenced number sequences.  |
| TAP (Test of attentional performance)           | tap_0011 – tap_0100   | median of the reaction time. (runs without warning tone); standard deviation of the reaction  |

|  |  |   |
|--|--|---|
|  |  | time. (runs without warning tone); number of omissions in the sustained attention task; number of omissions of auditory stimuli; number of omissions of visual stimuli. |
| LPS 50+
(Leistungsprüfungssystem
(performance testing
system) for 50 to 90 years
old)  | lps_0010 – lps_0040  | number of correctly solved lines.   |
| TMT-A / B, Trail Making
Test A / B  | tmt_0011 – tmt_0060  | number of seconds to complete the task A; number of seconds to complete the task B; TMT B/A ratio = time TMT-A / time TMT-B   |
| RWT, Regensburger
Wortflüssigkeits-Test
(Regensburg Word
Fluency Test)  | rwt_0011 – rwt_0080  | number of animals or first names mentioned within 60 seconds; number of S-words or M-words mentioned within 60 seconds.   |
| WST, Wortschatz-Test
(Vocabulary test)  | wst_0010-wst_0050  | raw score (sum of correct values)   |
| Biomarker related
endpoints   |  |   |
| biomarkers of
autoimmune activity
(autoantibody titers
against neurotransmitter
receptors; among others
β2-adeno-receptor- and
muscarine- receptor-
antibodies),
autoantibodies against
known or unknown
neuronal epitopes | stoe_0023-stoe_0025, ak_0011-ak_0063                       |   |
| immunostatus (differential
blood, IgG, IgM, IgA
fractions)   | ig_0011-ig_0063  |   |
| immunoglobulin levels
(including SARS-CoV-2
antibody titers and PCR, if
applicable)   | inf_0121-inf_0140, imh_0011, imh_0012, ig_0011-
ig_0023 |   |

|  |  |  |
|--|--|--|
| inflammatory biomarkers in blood (CRP, ferritin, MBL, white blood cell count, complement factors, immunoglobulin level and subtype)  | inf_0161-inf_0173  |  |
| neurofilament (NFL)  | liq_0161-liq_0163, liq_0171-liq_0173   |  |
| auto-antibody and vaccine titers in serum and cerebrospinal fluid as well as intrathecal synthesis (CFS)   | ak_0011-ak_0063  |  |
| inflammatory biomarkers in serum and cerebrospinal fluid (white cell count, total protein, CSF/serum quotients of albumin (Qalb), lactate, oligoclonal IgG bands (OCB), cytokines))  | haem_0051-haem_0273, chem_0011-chem_0083, liq_0011-liq_0173  |  |
| MRI measures: grey matter volume, white matter volume, thalamus volume left and right, thalamic functional connectivity to sensomotoric cluster left and right, thalamic functional connectivity to visuo-occipital cluster left and right, EndoPAT Reactive Hyperemia Index (RHI) | gm_volume, wm_volume, thalamus_l_volume, thalamus_r_volume, thalamic_motor_l_fc, thalamic_motor_r_fc, thalamic_occipital_l_fc, thalamic_occipital_r_fc, endopat_rhi  |  |
| OCT: ganglion cell-inner plexiform layer (GCIPL), peripapillary retinal nerve fiber layer (pRNFL), foveal avascular zone (FAZ), vessel density   | gcipl, prnfl, faz, vessel_density_full   |  |
| CD11c Expressions (CD19+ B cells, IgD-CD27+ memory B cells), IgM Expressions, Activated canonical class-switched memory B cells  | z_cd11c_exp_cd19pl, z_cd11c_exp_igdmin_cd27plus_cd19pl, perc_cd11cpl_cd19pl, perc_cd11cpl_igdmin_cd27pl_cd19pl, z_igm_exp_cd19pl, z_igm_exp_igdmin_cd27pl_cd19pl, perc_igmpl_cd19pl, perc_igmpl_igdmin_cd27pl_cd19pl, perc_acsm_igdmin_igmmmin_cd27pl_cd11cmin_cd19pl, perc_cl_acsm_igdmin_cd27pl_cd19pl |  |
| Safety related endpoints   |  |  |

|  |                   |  |
|--|-------------------|--|
| Adverse events and severe adverse events | ae_0053, sae_0123 |  |
|--|-------------------|--|

